9.1 Informed consent

Informed consent is the process of working with participants so that they fully understand what will and may happen to them while participating in a research study. The HVTN informed consent form documents that a participant (1) has been informed about the potential risks, benefits, and alternatives to participation, and (2) is willing to participate in an HVTN study. Informed consent encompasses all written or verbal study information HVTN CRS staff provide to the participant, before and during the trial. HVTN CRS staff will obtain informed consent of participants according to HVTN policies and procedures.

The informed consent process continues throughout the study. Key study concepts should be reviewed periodically with the participant and the review should be documented. At each study visit, HVTN CRS staff should consider reviewing the procedures and requirements for that visit and for the remaining visits. Additionally, if any new information is learned that might affect the participants' decisions to stay in the trial, this information will be shared with trial participants. If necessary, participants will be asked to provide revised informed consent.

An HVTN CRS may employ recruitment efforts prior to the participant consenting. For example, some HVTN CRSs use a telephone script to prescreen people before they come to the clinic for a full screening visit. Participants must sign a screening or protocol-specific consent before any procedures are performed to determine eligibility. HVTN CRSs must submit recruitment and prescreening materials to their IRB/EC and any applicable regulatory entity (RE) for human subjects protection review and approval.

Note: An RE is "Any group other than the local IRB/EC responsible for reviewing and/or approving a clinical research protocol and site-specific ICFs [informed consent forms] prior to implementation at a site." CRSs are responsible for knowing the requirements of their applicable REs.

9.1.1 Screening consent form

Some HVTN CRSs have approval from their IRB/EC and any applicable RE to use a general screening consent form that allows screening for an unspecified HIV vaccine trial. In this way, HVTN CRS staff can continually screen potential participants and, when needed, proceed quickly to obtain protocol-specific enrollment consent. Sites conducting general screening or prescreening approved by their IRB/EC and any applicable RE may use the results from this screening to determine eligibility for this

protocol, provided the tests are conducted within the time periods specified in the eligibility criteria.

9.1.2 Protocol-specific consent forms

The protocol-specific consent forms describe the study products to be used and all aspects of protocol participation, including screening and enrollment procedures. A sample protocol-specific consent form for the main study is located in Appendix A. A separate sample consent form for other uses of specimens is located in Appendix C.

Each HVTN CRS is responsible for developing a protocol-specific consent form(s) for local use, based on the sample protocol-specific consent forms in Appendix A and Appendix C. The consent form(s) must be developed in accordance with requirements of the following:

- CRS's IRB/EC and any applicable REs,
- CRS's institution, and
- Elements of informed consent as described in Title 45, CFR Part 46 and Title 21 CFR, Part 50, and in the International Conference on Harmonisation (ICH) E6, Good Clinical Practice: Consolidated Guidance 4.8.

Study sites are strongly encouraged to have their local CABs review their site-specific consent forms. This review should include, but should not be limited to, issues of cultural competence, local language considerations, and the level of understandability.

The sample informed consent form includes instructions throughout the document for developing specific content.

Sites should follow the instructions in the Protocol-specific Official Memo distributed along with this protocol regarding when they may begin using their site-specific protocol consent forms.

9.1.3 Assessment of Understanding

Study staff are responsible for ensuring that participants fully understand the study before enrolling them. This process involves reviewing the informed consent form with the participant, allowing time for the participant to reflect on the procedures and issues presented, and answering all questions completely.

An Assessment of Understanding is used to document the participant's understanding of key concepts in this HIV vaccine trial and that in a previous trial there was an association of increased HIV acquisition with receipt of that study vaccine. The participant must complete the Assessment of Understanding before enrollment. Staff may provide assistance in reading and understanding the questions and responses, if necessary. Participants must verbalize understanding of all questions answered incorrectly. This process and the participant's understanding of the key concepts should be recorded in source documentation at the site.

IRB/EC and any applicable RE may require that a participant has signed either a screening or protocol-specific consent document prior to administering the Assessment of

Understanding. The consent process (including the use of the Assessment of Understanding) should be explained thoroughly to the IRB/EC and any applicable RE, whose recommendations should be followed.

9.2 Pre-enrollment procedures

Screening may occur over the course of several contacts/visits, up to and including before vaccination on day 0. All inclusion and exclusion criteria must be assessed within 45 days before enrollment, unless otherwise specified in the eligibility criteria (or below in this section).

After the appropriate informed consent has been obtained and before enrollment, the following procedures are performed:

- Medical history, documented in the case history record;
- Assessment of Understanding (see Section 9.1.3);
- Assessment of risk for HIV infection
- Complete physical examination, including height, weight, vital signs, and clinical assessments of head, ears, eyes, nose, and throat; neck; lymph nodes; heart; chest; abdomen; extremities; neurological function; and skin;
- Assessment of concomitant medications the volunteer is taking, including
 prescription and nonprescription drugs, vitamins, topical products,
 alternative/complementary medicines (eg, herbal and health food supplements),
 recreational drugs, vaccinations, and allergy shots;
- Laboratory tests as defined in the inclusion and exclusion criteria, including:
 - Screening HIV testing at local lab,
 - Pregnancy test,
 - Hemoglobin;
- Obtaining of volunteer demographics in compliance with the NIH Policy on Reporting Race and Ethnicity Data: Subjects in Clinical Research, Aug. 8, 2001 (available at http://grants.nih.gov/grants/guide/notice-files/NOT-OD-01-053.html);
- Counseling on HIV testing and risk reduction, as described in Section 9.7; and
- Discussion of pregnancy prevention. A pregnant or breastfeeding person may not be enrolled in this trial. Specific criteria and assessment of contraception and pregnancy status are described in study inclusion criteria.

9.2.1 Use of screening results from another HVTN study

If a participant screens for an HVTN study at the same HVTN CRS but then does not join that study, screening results from that effort may be applied to the screening for this protocol, as long as the screening was done under participant consent, the participant has signed a consent form to begin screening for this study, and the tests were conducted within the time periods specified in the eligibility criteria (see Sections 7.1 and 7.2).

9.3 Enrollment and vaccination visits

Enrollment is simultaneous with first vaccination. The time interval between randomization and enrollment should not exceed 4 working days. The HVTN CRS registers the participant by scheduling the day 0 visit (enrollment) via the Web-based randomization system, and requests the randomization assignment. Circumstances may require a participant's enrollment visit to be changed. This may exceed the 4-day randomization time limit.

At all vaccination visits, the following procedures are performed before vaccination:

- Abbreviated physical examination, including weight, vital signs, and a symptomdirected evaluation by history and/or appropriate physical exam based on participant self-reported symptoms or complaints;
- Assessment of baseline reactogenicity parameters;
- Assessment of concomitant medications (as described in Section 9.2);
- Assessment of any new or unresolved AEs/ intercurrent illnesses;
- Confirm that participants received HIV test results from previous visit. If not provide test results and post-test counseling as appropriate;
- Pregnancy test. Persons who are NOT of reproductive potential due to having undergone total hysterectomy or bilateral oophorectomy (verified by medical records), are not required to undergo pregnancy testing; and
- Specimen collection as applicable.

Following completion of all procedures in the preceding list, and if results indicate that vaccination may proceed, vaccination is prepared and administered (see Sections 8.3 and 8.4).

Administration of all injections during a vaccination visit must be accomplished within 1 calendar day.

Immediately following vaccination, the participant remains in the clinic for observation. An initial reactogenicity assessment is made at a target of 30 minutes after injection, with an acceptable range of 25-60 minutes. Before leaving the clinic, the participant is given a postvaccination memory tool and is instructed on how to complete it. The site will make arrangements to obtain a report of reactogenicity events from the participant after the reactogenicity period (as described in Section 9.9).

The following procedures will be performed at all vaccination visits. These procedures may be performed prior to or following vaccination:

- Risk reduction counseling (as described in Section 9.7);
- Pregnancy prevention assessment (as described in Section 9.2 and 9.8);
- Assessment of new or unresolved social impacts (site staff will ask participant about
 the status of any unresolved social impacts and if she has experienced any new social
 impacts as a result of the trial participation).

Additional procedures will be performed at scheduled visits as specified in Appendix G:

- Gonorrhea and Chlamydia trachomatis (GC/CT) testing (before vaccination);
- Trichomonas vaginalis testing (before vaccination);
- Syphilis testing (before vaccination);
- Microbiome/mucosal collections: vaginal swab and cervical cup (before vaccination);
- Behavioral risk assessment questionnaire;
- Outside testing and belief questionnaire; and
- HIV infection assessment.

9.4 Follow-up visits

The following procedures are performed at all scheduled follow-up visits:

- Risk reduction counseling (as described in Section 9.7);
- Assessment of new or unresolved social impacts (site staff will ask participant about
 the status of any unresolved social impacts and if s/he has experienced any new
 social impacts as a result of the trial participation);
- Specimen collection as applicable;
- Assessment of new or continuing concomitant medications (as described in Section 9.2); and
- Assessment of new or unresolved AEs/intercurrent illnesses.

Additional procedures will be performed at scheduled follow-up visits as specified in Appendix E and Appendix G:

- Pregnancy prevention assessment (as described in Section 9.2 and 9.8);
- Microbiome/mucosal collections: vaginal swab and cervical cup (before vaccination);
- GC/CT testing;
- Trichomonas vaginalis testing;
- Syphilis testing;
- Abbreviated physical examination, including weight, vital signs, and a symptomdirected evaluation by history and/or appropriate physical exam based on participant self-reported symptoms or complaints;
- Complete physical examination, including height, weight, vital signs, and clinical assessments of head, ears, eyes, nose, and throat; neck; lymph nodes; heart; chest; abdomen; extremities; neurological function; and skin;
- HIV infection assessment including pre-test counseling. A subsequent follow-up contact is conducted to provide post-test counseling and to report results to participant;
- Confirm that participants received HIV test results from previous visit. If not, provide test results and post-test counseling as appropriate;
- Behavioral risk assessment questionnaire;

- Outside Testing and Belief Questionnaire; and
- Urine pregnancy test. Persons who are NOT of reproductive potential due to having undergone total hysterectomy or bilateral oophorectomy (verified by medical records), are not required to undergo pregnancy testing.

9.5 Procedures for HIV-infected participants

The following procedures are performed at follow-up visits for HIV-infected participants, as specified in Appendix F and Appendix H:

- Counseling on HIV-1 testing/diagnosis;
- Referral to medical professionals for care;
- Abbreviated physical examination including weight, vital signs, and a symptomdirected evaluation by history and/or appropriate physical exam based on participant self-reported symptoms or complaints;
- Complete physical examination, including clinical assessments of head, ears, eyes, nose, and throat; neck; lymph nodes; heart; chest; abdomen; extremities; neurological function; and skin;
- Assessment of HIV/AIDS-related conditions and non-HIV disease progressionrelated events;
- Assessment of new or continuing concomitant medications (as described in 9.2);
- Assessment of new or continuing antiretroviral therapies and reason for initiation or change in therapy;
- Assessment of new or unresolved AEs/intercurrent illnesses;
- Counseling to reduce the risk of HIV transmission;
- Administration of behavioral risk assessment questionnaire;
- Assessment of new or unresolved social impacts (site staff will ask participant about the status of any unresolved social impacts and about any new social impacts experienced as a result of the trial participation);
- Specimen collection (Appendix F).

9.6 Mucosal sampling

Vaginal swabs and cups will be collected from study participants at the visits indicated in Appendix E and Appendix G. These samples will be used for vaginal microbiome analysis and assessment of markers of inflammation including but not limited to cytokines, chemokines and other soluble mediators.

9.7 HIV counseling and testing

HIV counseling will be performed in compliance with the CDC's guidelines or other local guidelines for HIV counseling and referral. HIV testing will be performed in accordance with the current HVTN HIV testing algorithm following enrollment.

Participants will be counseled routinely during the trial on the avoidance of HIV infection and on the potential negative social impacts of testing antibody positive due to the vaccine. They will also be counseled on the risks of HIV antibody testing outside of the HVTN CRSs and will be discouraged from doing so during study participation and/or during any period of vaccine-induced positive serology.

Study staff will take particular care to inform study participants of the likelihood of routine HIV testing being offered or performed outside the study CRS at emergency rooms, clinics, and medical offices. CRS staff should inform participants of their right to opt out of HIV testing outside the study site. CRS staff should inform study participants if regulations permit medical providers to perform HIV testing without first informing patients. If this is the case, then CRS staff should advise study participants that they may decline testing preemptively. CRS staff should also inform participants if positive results must be reported to local public health authorities. CRS staff should also inform participants of the need to maintain study blinding by getting HIV testing only at the study CRS. CRS staff should provide participants with CRS contact information and should encourage participants to ask medical providers to contact the CRS. The CRS can verify that the participant is in an HIV vaccine clinical trial and should only be tested at the study CRS.

Potential participants identified as being HIV infected during screening are not enrolled. All participants who are identified as being HIV infected during the study will be followed for approximately 6 months as detailed in Appendix F and Appendix H.

9.7.1 Distinguishing intercurrent HIV infection from vaccine-induced positive serology

The study product may elicit an antibody response to HIV proteins. Therefore, vaccine-induced positive serology may occur in this study. Several precautionary measures will be taken to distinguish intercurrent HIV infection from vaccine-induced positive serology. These precautionary measures include:

- Participants will have physical examinations at visits specified in Appendix G. Signs
 or symptoms of an acute HIV infection syndrome, an intercurrent illness consistent
 with HIV-1 infection, or probable HIV exposure (ie, unprotected sex with a known
 HIV positive partner), would prompt a diagnostic workup per the HVTN algorithm
 for Recent Exposure/Acute Infection Testing to determine HIV infection.
- HIV testing will be performed at multiple timepoints throughout the study (see Appendix E and Appendix G). The Laboratory Program (or approved diagnostic laboratory) will follow the HVTN HIV testing algorithm (as described in the HVTN Laboratory Manual of Operations), which is able to distinguish vaccine-induced antibody responses from actual HIV infections.
- All participants can receive HIV-1 diagnostic testing from the site following their last scheduled visit until they are told that they did not receive an HIV vaccine
- All participants who received vaccine product and who have vaccine-induced positive or indeterminate HIV-1 serology (as measured by the standard anti-HIV

antibody screening tests) at or after the study is unblinded will be offered poststudy HIV-1 diagnostic testing (per the HVTN poststudy HIV-1 testing algorithm) periodically and free of charge as medically/socially indicated (approximately every 6 months) unless or until HIV antibody testing is no longer the standard test in clinical settings.

9.7.2 VISP registry

Experimental HIV vaccines may induce antibody production to HIV antigens, producing reactive results on commercially available HIV test kits. This is called "vaccine-induced seropositivity" (VISP). In order to provide poststudy HIV testing to distinguish between VISP and HIV infection, and to mitigate potential social harms resulting from VISP in HIV vaccine recipients who are not infected with HIV, the HVTN has created a VISP registry. Following study unblinding, the registry will allow trained staff to verify that an individual has received an HIV vaccine, and therefore has the potential for VISP. Information in the VISP registry will not be used for research. Rather, the registry exists to support provision of poststudy testing and counseling services to HIV vaccine recipients. The registry contains the names of all study participants, unless they request that their names be removed.

9.8 Pregnancy prevention assessment

Contraception status is assessed and documented at scheduled clinic visits as specified in Appendix G for a participant who is sexually active in a way that could cause that participant to become pregnant. Prior to enrollment and throughout the study, staff will ask participants to verbally confirm their use of adequate contraceptive methods. A participant who is sexually active in a way that could cause that participant to become pregnant should be reminded at scheduled clinic visits, specified in Appendix G, of the importance of using contraception and should be referred to specific counseling, information, and advice as needed. (Specific contraception requirements are listed in Section 7.1). This reminder should be documented in the participant's study record.

Self-reported infertility—including having reached menopause (no menses for 1 year) or having undergone hysterectomy, bilateral oophorectomy, or tubal ligation—must be documented in the participant's study record.

9.9 Assessments of reactogenicity

For all participants, baseline assessments are performed before and reactogenicity assessments are performed after each vaccination. All reactogenicity symptoms are followed until resolution and graded according to the Division of AIDS Table for Grading the Severity of Adult and Pediatric Adverse Events, Corrected Version 2.1, July 2017, except as noted in Section 12.2.2.

The reactogenicity assessment period is 3 full days following each vaccination. At some sites the reactogenicity assessment period may be 7 full days following each vaccination. The maximum severity reached for each symptom during the assessment period is reported on CRFs. Participants will be given a postvaccination memory tool to assist with recall of symptoms. The site staff and the participant will make multiple efforts in good faith to be in contact after the last day of the reactogenicity period, or sooner if indicated,

to review reactogenicity data. Clinic staff will follow new or unresolved reactogenicity symptoms present at the last day of the reactogenicity assessment period to resolution. Participants are instructed to contact the clinic for events that arise during the period between vaccination and the next scheduled visit. In general, a participant who self-reports any postvaccination reaction greater than mild is seen by a clinician within 48 hours after onset, unless the reaction is improving and/or has resolved completely.

Reactogenicity assessments include assessments of systemic and local symptoms and vaccine-related lesions. Events not listed on a CRF, or with an onset after the reactogenicity assessment period, or those meeting SAE/AEs criteria requiring expedited reporting, are recorded on an AE log form.

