5.1 Primary objectives and endpoints

Primary objective 1:

To evaluate the preventive vaccine efficacy (VE) of a heterologous prime/boost regimen utilizing Ad26.Mos4.HIV and aluminum-phosphate adjuvanted Clade C gp140 for the prevention of HIV infection in HIV-seronegative women residing in sub-Saharan Africa from confirmed HIV-1 infections diagnosed between the Month 7 and Month 24 visits

Primary endpoint 1:

Vaccine efficacy as derived from confirmed HIV-1 infections diagnosed between the Month 7 and Month 24 visits

Primary objective 2:

To evaluate the safety and tolerability of a heterologous prime/boost regimen utilizing Ad26.Mos4.HIV and aluminum-phosphate adjuvanted Clade C gp140 for the prevention of HIV infection in HIV-seronegative women residing in sub-Saharan Africa

Primary endpoint 2:

Local and systemic reactogenicity signs and symptoms for 3 days after each vaccination, adverse events for 30 days after each vaccination, and serious adverse events, AESIs, and adverse events leading to early participant withdrawal or early discontinuation of study product(s) administration for the entire duration of the study.

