5.3 Exploratory objectives

Exploratory objective 1:

To evaluate vaccine effects ("vaccine activity") on virologic and immunologic outcomes (eg, HIV-1 viral load (VL) and postdiagnosis CD4+ T-cell count) among HIV-1-infected participants for 6 months post diagnosis accounting for ARV use

Exploratory objective 2:

To explore the association between the vaginal microbiome as well as genital inflammation, and HIV infection risk

Exploratory objective 3

To evaluate early and innate immune responses (eg, whole blood transcriptomics, serum cytokines) one day after the third vaccination (ie, the first protein boost) as correlates of risk of subsequent HIV acquisition

Exploratory objective 4:

To evaluate local and systemic reactogenicity signs and symptoms that arise from day 4 to day 7 at a subset of clinical research sites

Exploratory objective 5:

To further evaluate the immunogenicity of the vaccine regimen, additional immunogenicity assays may be performed, and assays may be performed on samples from other timepoints, based on the HVTN Laboratory Assay Algorithm

Exploratory objective 6:

To assess use of biomedical interventions and biological and behavioral factors in the study cohort and how they modify vaccine efficacy

Exploratory objective 7:

To evaluate the role of host genetic factors in the immune response to the vaccine regimen and in vaccine effects on study endpoints

Exploratory objective 8:

To perform comparative analyses of correlates of risk identified in HVTN 705 and those identified in other HIV vaccine efficacy studies

Exploratory objective 9:

To conduct analyses related to furthering the understanding of HIV, immunology, vaccines, and clinical trial conduct

6 Statistical considerations

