### **7.1.1 Reactogenicity**

The number and percentage of participants experiencing each type of reactogenicity sign or symptom will be tabulated by severity, treatment group and the length of reactogenicity follow-up (3 days versus 7 days) and the percentages will be displayed graphically by arm and the length of reactogenicity follow-up (3 days versus 7 days). For a given sign or symptom, each participants reactogenicity will be counted once under the maximum severity for each injection visit. In addition, to the individual types of events, the maximum severity of local pain or tenderness, induration or erythema, and of systemic symptoms will be calculated. Kruskal-Wallis tests will be used to test for differences in severity between arms.

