**Table RE1. Maximum Local Reactogenicity by Treatment Assignment**  
**Population: Full Analysis Set (N = xxx)**

	Total (N=xxx)	A 3 Day* (N=xxx)	B 3 Day* (N=xxx)	A 7 Day* (N=xxx)	B 7 Day* (N=xxx)
Pain					
None	xxx (xx.x%)	xxx (xx.x%)	xxx (xx.x%)	xxx (xx.x%)	xxx (xx.x%)
Mild	xxx (xx.x%)	xxx (xx.x%)	xxx (xx.x%)	xxx (xx.x%)	xxx (xx.x%)
Moderate	xxx (xx.x%)	xxx (xx.x%)	xxx (xx.x%)	xxx (xx.x%)	xxx (xx.x%)
Severe	xxx (xx.x%)	xxx (xx.x%)	xxx (xx.x%)	xxx (xx.x%)	xxx (xx.x%)
Potentially Life-Threatening	xxx (xx.x%)	xxx (xx.x%)	xxx (xx.x%)	xxx (xx.x%)	xxx (xx.x%)
Tenderness					
None	xxx (xx.x%)	xxx (xx.x%)	xxx (xx.x%)	xxx (xx.x%)	xxx (xx.x%)
Mild	xxx (xx.x%)	xxx (xx.x%)	xxx (xx.x%)	xxx (xx.x%)	xxx (xx.x%)
Moderate	xxx (xx.x%)	xxx (xx.x%)	xxx (xx.x%)	xxx (xx.x%)	xxx (xx.x%)
Severe	xxx (xx.x%)	xxx (xx.x%)	xxx (xx.x%)	xxx (xx.x%)	xxx (xx.x%)
Potentially Life-Threatening	xxx (xx.x%)	xxx (xx.x%)	xxx (xx.x%)	xxx (xx.x%)	xxx (xx.x%)
Pain and/or Tenderness					
None	xxx (xx.x%)	xxx (xx.x%)	xxx (xx.x%)	xxx (xx.x%)	xxx (xx.x%)
Mild	xxx (xx.x%)	xxx (xx.x%)	xxx (xx.x%)	xxx (xx.x%)	xxx (xx.x%)
Moderate	xxx (xx.x%)	xxx (xx.x%)	xxx (xx.x%)	xxx (xx.x%)	xxx (xx.x%)
Severe	xxx (xx.x%)	xxx (xx.x%)	xxx (xx.x%)	xxx (xx.x%)	xxx (xx.x%)
Potentially Life-Threatening	xxx (xx.x%)	xxx (xx.x%)	xxx (xx.x%)	xxx (xx.x%)	xxx (xx.x%)
Erythema					
None / Not Gradable	xxx (xx.x%)	xxx (xx.x%)	xxx (xx.x%)	xxx (xx.x%)	xxx (xx.x%)
Gr 1: 2.5 - <5 cm / 6.25 - < 25cm 	xxx (xx.x%)	xxx (xx.x%)	xxx (xx.x%)	xxx (xx.x%)	xxx (xx.x%)
Gr 2: 5 - <10cm / 25 - <100cm 	xxx (xx.x%)	xxx (xx.x%)	xxx (xx.x%)	xxx (xx.x%)	xxx (xx.x%)
Gr 3: >=10cm / >=100cm  /	xxx (xx.x%)	xxx (xx.x%)	xxx (xx.x%)	xxx (xx.x%)	xxx (xx.x%)
Complications					
Gr 4: Complications	xxx (xx.x%)	xxx (xx.x%)	xxx (xx.x%)	xxx (xx.x%)	xxx (xx.x%)
.					
.					
.					

Participants are counted once per reactogenicity sign/symptom according to the maximum severity level experienced across all vaccinations.

\*Participants for which 7-day reactogenicity data are collected are only shown in the respective columns (7 Day). Their reactogenicity in the first 3 days is not reflected together with the rest of 3-Day reactogenicity data.

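### As described, the plan gives neither 3-day reactogenicity for the full analysis set nor an analysis of symptoms arising on days 4 to 7

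*Protocol*

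**What the plan says.** Protocol 5.1 defines the reactogenicity part of primary endpoint 2 as "Local and systemic reactogenicity signs and symptoms for 3 days after each vaccination". Protocol 5.3 gives exploratory objective 4 as "To evaluate local and systemic reactogenicity signs and symptoms that arise from day 4 to day 7 at a subset of clinical research sites".

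Protocol 9.9 describes the data. The default is "The reactogenicity assessment period is 3 full days following each vaccination", but "At some sites the reactogenicity assessment period may be 7 full days following each vaccination". For both, "The maximum severity reached for each symptom during the assessment period is reported on CRFs". Events that start after the assessment period go to the adverse event log.

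On analysis, Protocol 6.1 and SAP section 7 place safety on the FAS. SAP 7.1.1 has reactogenicity "tabulated by severity, treatment group and the length of reactogenicity follow-up (3 days versus 7 days"), counting each participant once at maximum severity per injection visit. SAP section 9, items 5(a) and 5(b), carries the same split into the end-of-Stage-1 report. Mock Tables RE1 and RE2 in SAP Appendix A have one Total column and separate 3-day and 7-day columns by arm. Their footnote says that 7-day participants appear only in the 7-day columns, and adds: "Their reactogenicity in the first 3 days is not reflected together with the rest of 3-Day reactogenicity data".

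**The concern.** The protocol names two windows, days 0-3 for a primary endpoint and days 4-7 for an exploratory objective. The record it describes at 7-day sites is a single maximum over both. The SAP's response is to separate participants by how long they were followed, which is a different thing from separating symptoms by when they occurred.

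At stake is whether the primary safety summary matches its own definition for every woman in the FAS, and whether the longer follow-up at selected sites yields the information for which objective 4 was written.

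**Working it through.** The plan states no figure on this point, so the check is mainly one of definitions.

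**1. What a 7-day maximum can tell.** For one symptom and one vaccination, let M03 be the maximum severity on days 0-3 and M47 the maximum on days 4-7. The described record is M7 = max(M03, M47).
- If M7 is none, both windows are known to be none.
- If M7 is any grade g above none, all that is known is that neither window exceeded g and at least one reached it.

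Two women at a 7-day site show this:

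| | Day 1 | Day 5 | M03 (primary endpoint 2) | M47 (objective 4) | Recorded M7 |
|---|---|---|---|---|---|
| A | moderate headache, resolves | none | moderate | none | moderate |
| B | none | moderate headache | none | moderate | moderate |

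The records are identical although the two women differ on both the endpoint and the objective. Because M7 is never below M03, the 7-day columns give only an upper bound for 3-day reactogenicity at each severity threshold.

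**2. The same events at a 3-day site.** Woman A has moderate on the reactogenicity form. Woman B has none there, and her day 5 headache goes to the adverse event log because it began after the period ended. The day 4-7 event is thus handled differently by site type, and at 7-day sites no onset day is described for it.

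**3. What the tables deliver.**
- 3-day columns: M03, for women at 3-day sites only.
- 7-day columns: M7, for women at 7-day sites only.
- Total: as laid out, M03 from some women pooled with M7 from others, which is neither window.

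No column gives M03 for the whole FAS and none gives M47 or day 4-7 onset for anyone.

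**4. Is objective 4 analysed elsewhere?** SAP 8.3 to 8.5 are headed for exploratory objectives 1 to 3, and no section follows for objective 4. Setting 7-day sites against 3-day sites would be indirect and confounded with site, since the length of follow-up is not randomized.

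**5. How many women.** Neither document gives the number of 7-day sites or their share of participants. With 1300 per arm (Protocol Table 3-1) and an assumed share f, the women with only M7 number 1300 × f per arm:
- f = 0.10: 130 per arm, leaving 1170 in the 3-day columns.
- f = 0.30: 390 per arm, leaving 910.

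**6. Is the arm comparison affected?** Protocol 6.7 stratifies randomization by site, so vaccine and placebo are balanced within 3-day sites and within 7-day sites. Each by-arm contrast is fair for the window it uses.

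**The case against.** The strongest reply is that the case report form is not among the documents. Protocol 9.9 says that the maximum is reported, without saying that nothing else is. Some timing is clearly observed: temperature is taken daily (9.9.1), injection site areas above 25 cm² are followed daily (9.9.2), symptoms are followed to resolution, and a footnote to Table 12-1 uses a 3-day duration. The RE1/RE2 footnote can also be read as a display choice about data that exist, and those tables are shells for the DSMB closed report. This stands against any claim that objective 4 is unanswerable. It does not supply a data path: no passage says that onset day or daily severity of symptoms is entered, and section 9 carries the split by follow-up length into the primary report.

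Three stronger readings are tempting and not supported.
- A reader might infer that women at 7-day sites drop out of the primary safety endpoint. They remain in the FAS, have their own by-arm columns, and stay in the adverse event, serious adverse event and AESI analyses that make up the rest of primary endpoint 2. Their 7-day maximum still includes the first 3 days, so no reaction inside the window is lost.
- A reader might quote a loss of precision of about 5% to 20%, from 1/√0.9 = 1.05 and 1/√0.7 = 1.20. That rests on an assumed share and on confidence intervals that the plan does not specify; Protocol 6.9.3.1 and SAP 7.1.1 plan counts, percentages and Kruskal-Wallis tests.
- A reader might infer that the postvaccination memory tool already holds day-by-day data. Protocol 9.9 describes it only as a recall aid.

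It is also fair that objective 4 is one of nine exploratory objectives, at an optional subset of sites.

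**Conclusion.** The point holds as a mismatch between endpoint definitions and the data and tables described. Primary endpoint 2's 3-day reactogenicity is not reported for the full FAS, the Total column pools 3-day and 7-day maxima, and exploratory objective 4 has no analysis that isolates days 4 to 7. It is a matter of endpoint definition and completeness; it introduces no bias between arms.

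Its size cannot be fixed from the documents, because the share of women at 7-day sites is not stated; the 130 to 390 per arm above is illustrative. The conclusion assumes that the protocol's description of the form is complete. If onset day or daily severity is in fact captured, the gap is in the SAP alone and can be closed by derivation. The change is worth making because a primary safety endpoint is involved and the remedy is cheap.

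**What to change.** 1. State whether the form captures onset day or daily severity for symptoms at 7-day sites. If so, derive the day 0-3 maximum and day 4-7 onset from it.
2. If not, enter two maxima per symptom and vaccination at those sites, one for days 0-3 and one for days 4-7. An overall maximum plus onset day is an alternative, but it does not recover the day 0-3 maximum when a symptom starts early and worsens after day 3.
3. In SAP 7.1.1, section 9 items 5(a)-(b) and Tables RE1/RE2, tabulate the day 0-3 maximum from all sites by arm on the full FAS for primary endpoint 2. Report day 4-7 onset by arm at 7-day sites for objective 4. If only the two maxima exist, define onset as none on days 0-3 and some on days 4-7.
4. Where the split can no longer be collected, state the limitation and reword objective 4 as a 7-day maximum by arm. This may well apply: SAP section 9 puts the last Month 24 target visit at 25 May 2021, so the last scheduled Month 12 vaccination fell about a year earlier.

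The cost is a derivation, or at most one extra field per symptom at 7-day sites with slightly more data entry, plus revised table shells.
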